## Chapter 1: Overview of Study Design

### **1.1 Study Objectives**

This study will combine, adapt and test motivational interviewing (MI) and the Community Reinforcement Approach (CRA) as a culturally congruent treatment approach for Native Americans. The proposed developmental research will be conducted in collaboration with the Southwest Native American Tribe. The specific aims of this project are:

Aim 1. To develop, in collaboration with the Southwest Native American community, a combination of MI and CRA (MICRA) that is culturally adapted to the social/cultural context of reservation-dwelling tribal members and includes a secondary focus on HIV/STD prevention

Aim 2. To develop and field test culturally-congruent research materials and procedures (MICRA counselor manual, adapted assessment instruments, manual of operations) that would be needed for a larger clinical trial of MICRA with Southwest Native American or other tribal populations

Aim 3. To train Southwest Native American behavioral health professionals in delivery of MICRA, and pilot test procedures for MICRA certification, supervision, and fidelity assurance

Aim 4. To conduct a pilot study (N=80) to estimate effect sizes for MICRA on key outcome variables with Southwest Native American clients

Aim 5. To estimate the types and prevalence of emotional distress and psychological and health problems likely to be encountered when treating substance use disorders in Native American populations.

### **1.2 Study Design**

MICRA will be conducted in two phases: Phase 1 is a feasibility ( $N = 9$ ) non-randomized one-group design wherein all participants will receive MICRA. The purpose of Phase 1 is to (a) implement and test the draft version of the MICRA counselor manual, (b) test counselor fidelity monitoring procedures, (c) certify counselors in MI and CRA, (d) test the assessment procedures and basic aspects of the MOO, (e) certify the research assistant in assessment administration procedures, and (e) pilot the 4- and 8-month follow-ups.

Phase 2 is a pilot ( $N = 80$ ) 2-group design. Following the screening and baseline interview, participants will be randomized to receive MICRA or treatment as usual (TAU; see Chapter 5 for randomization process). Participants randomized to MICRA will receive from 16 to 20 therapy sessions with one of the MICRA counselors over the course of 16 weeks. In TAU, participants will receive standard outpatient services at Southwest Native American Recovery Center.

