### 1.4.4 Treatment as Usual

Southwest Native American Recovery Center (SWNARC), the sole outpatient substance abuse treatment program in the Southwest Native American tribe, will serve as the treatment as usual (TAU) comparison for this study. Treatment provided by the Southwest Native American Recovery Center is fairly consistent in its approach. The intake staff assess all clients. Detailed histories are gathered, individual cases are staffed, and clinical assignments are made. Clients are assigned to counselors who have openings; there is no attempt to match client to counselor, other than with an eye towards gender. Treatment starts with individual sessions. Soon thereafter the client joins ongoing group sessions. The clinical staff usually runs group sessions (90 minutes on average), and they engage clients with a reflective style, encouraging them to share their stories regarding substances. Newer group members are generally quiet. From time to time, elder Southwest Native Americans will come to the group meeting and discuss either their personal struggle with substance abuse, or share Southwest Native American perspectives on treating all things - including the self- with respect. Examples of ongoing groups

include a men's group, women's group, arts and crafts group, and Triple A dance group. Individual counseling sessions (60 minutes on average) consist of listening and implementing a generally didactic style that compares current behavior with desired behavior, current situation with optimal situation. Individual sessions occur once weekly, but may happen more frequently if an individual is in crisis. 12 step principles are presented at SWNARC, but more in spirit than in substance. Family members are usually not included in counseling sessions. Individual sessions also review Southwest Native American traditional teachings, showing the client his or her place within the framework of Southwest Native American life. Three cultural educators are part of the SWNARC staff. Release from substance abuse treatment is based on clinical judgment. While clients can spend up to a year at SWNARC, the average length of treatment is two months.

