### **7.5 Data Analysis Plan**

The primary dependent measure of use derived from the Form 90 and the saliva drug tests will be percent days abstinent from: alcohol, amphetamine, cannabis, cocaine, and inhalants. Secondary outcomes measures include other self-report assessments such as self-reported days of substance use and oral saliva drug results, self-efficacy, negative consequences, cultural identity, microaggressions and sexual risk behaviors. Outcome data will be analyzed using two-group MANOVA comparing MICRA and TAU conditions on key dependent measures: (1) percent days abstinent from all substances of abuse as measured from timeline follow-back, and (2) level of substance related problems as measured by the InDUC. The endpoint for this analysis will be 4-month follow-up and baseline levels of the dependent measures will be entered as covariates. Later analysis will explore outcomes across 12 months post-randomization. Secondary analyses will employ hierarchical linear modeling (HLM) for modeling effects over time given we have at least 3 time points. Exploratory analyses will also encompass outcomes on secondary measures such as ASI, cultural identity, microaggressions, brief symptom inventory, and sexual risk behaviors. Alpha level will be set at .05. The study's statistician or PI will analyze these data using SPSS software and Amos.

*Appendix A*

**SOUTHWEST NATIVE AMERICAN MICRA PROJECT  
[name]  
[name]**

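### The MANOVA treats participants as independent although they share counselors, so if outcomes correlate within counselor the standard errors are too small and the .05 test too liberal

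*Protocol*

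**What the plan says.** On delivery in the experimental arm, section 1.2 gives each MICRA participant 16 to 20 sessions "with one of the MICRA counselors over the course of 16 weeks". Section 1.4.3 adds that these sessions are individual rather than group therapy.

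On the comparator, section 1.4.4 states: "Clients are assigned to counselors who have openings; there is no attempt to match client to counselor, other than with an eye towards gender". It also describes shared groups: "Soon thereafter the client joins ongoing group sessions".

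On analysis, section 7.5 states: "Outcome data will be analyzed using two-group MANOVA comparing MICRA and TAU conditions on key dependent measures". The two measures are percent days abstinent and the InDUC. It continues: "The endpoint for this analysis will be 4-month follow-up and baseline levels of the dependent measures will be entered as covariates". Alpha is .05. HLM is named as a secondary analysis, to model effects across the follow-up time points. No counselor or group term appears, fixed or random.

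Section 1.1, Aim 4, gives the purpose of the 80-participant pilot as estimating effect sizes. Section 5.1 sets 40 participants per condition.

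**The concern.** A MANOVA takes its error variance from differences between participants assumed to be independent. Here participants within an arm share a counselor, and a counselor who does better or worse than average moves a whole block of outcomes together. Several features make some counselor variation plausible. MICRA content is chosen from a menu rather than set session by session (section 1.4.3). Counselors are coached up to a criterion and retrained if they drift (section 5.5). A MICRA participant is taken to a counselor's office, or booked with a counselor if all are occupied (section 4.5), so counselors are not described as assigned at random.

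If the within-counselor correlation is positive, the point estimates are unaffected but their stated precision is too high, and the .05 test has a true error above .05. Effect-size estimation is an explicit aim of the pilot, so how well the effect is known is part of its product.

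The omission could also become hard to repair. The fields listed for the Tracking Log and the Participant Enrollment Log (section 5.4) include no counselor. Session recordings are labelled with participant ID, date and session number only, and are destroyed after coding (section 5.5). The referral form in Appendix A has a line for the assigned counselor, but section 2.3 uses that form to report attendance to outside agencies, not as research data.

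**Working it through.** The protocol gives no power, SD, ICC or interval width for N = 80, so there is no figure of its own to reproduce. The check asks how far the independence assumption could be off.

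**Inputs from the protocol**
- n = 40 per arm (section 5.1).
- Alpha .05 (section 7.5). Sidedness is not stated; two-sided is assumed.
- Follow-up of at least 80% as a benchmark (section 6.1), which gives 0.80 × 40 = 32 per arm.

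**Assumptions, because the protocol is silent**
- k = 2 to 4 MICRA counselors with equal caseloads.
- ICC 0.01 to 0.10.
- Clustering in the MICRA arm only.

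**Formulas**
- Participants per counselor: m = n/k.
- Design effect: DE = 1 + (m − 1) × ICC.
- Ratio of true to reported standard error: R = √((DE + 1)/2), with equal arms and TAU left at a design effect of 1.
- True two-sided error of the nominal .05 test: 2 × (1 − Φ(1.96/R)).

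**Central case, k = 3, ICC 0.05**
- m = 40/3 = 13.33.
- DE = 1 + 12.33 × 0.05 = 1.617.
- R = √(2.617/2) = 1.144.
- 1.96/1.144 = 1.713, so the true error is 0.087.

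**Range at 40 per arm, MICRA clustered only**

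| k | ICC | DE | R | True error |
|---|---|---|---|---|
| 4 | 0.01 | 1.09 | 1.022 | 0.055 |
| 4 | 0.05 | 1.45 | 1.107 | 0.077 |
| 4 | 0.10 | 1.90 | 1.204 | 0.104 |
| 3 | 0.01 | 1.123 | 1.030 | 0.057 |
| 3 | 0.05 | 1.617 | 1.144 | 0.087 |
| 3 | 0.10 | 2.233 | 1.271 | 0.123 |
| 2 | 0.01 | 1.19 | 1.046 | 0.061 |
| 2 | 0.05 | 1.95 | 1.214 | 0.107 |
| 2 | 0.10 | 2.90 | 1.396 | 0.160 |

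At ICC 0, DE = 1, R = 1 and the error is 0.05 for every k.

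**At 32 per arm**
- k = 3, ICC 0.05: m = 10.67, DE = 1.483, R = 1.114, true error 0.079.
- k = 2, ICC 0.10: R = 1.323, true error 0.138.

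**If TAU is clustered by counselor as well.** With the same k and ICC in both arms, R = √DE. For k = 3 and ICC 0.05 this is √1.617 = 1.271, with a true error of 0.123. The MICRA-only range is therefore the milder case.

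**Limits of the check.** This is a large-sample, single-outcome calculation with equal caseloads. The planned test is a joint one on two baseline-adjusted outcomes. The direction carries over to it, but the exact error rates do not.

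**The case against.** The strongest reply is that the size of the problem rests on two quantities absent from the protocol. At the low end (R 1.022, error 0.055) it is immaterial, and at ICC 0 it vanishes. The protocol also gives reasons to expect a modest ICC: a manual, counselor certification, taped adherence monitoring and retraining. All of that stands. The statement has to be conditional on a positive ICC, with the size given only as a range under stated assumptions.

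A second reply is that counselor effects belong in a separate analysis plan. That would be fair had section 7.5 left the model open. It names the model, outcomes, endpoint, covariates and alpha, and gives the HLM a different purpose. A separate plan could still add the sensitivity analysis, but the protocol as written points to independence.

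Several stronger readings are tempting and are not supported:

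- A reader might infer that the trial will report confidence intervals that are too narrow. The protocol specifies no intervals. The defect concerns the standard errors and the .05 test.
- A reader might infer that the effect sizes are meant to size a later trial, since Aim 2 speaks of what is "needed for a larger clinical trial of MICRA". That phrase refers to research materials and procedures. Aim 4, which concerns effect sizes, mentions no later trial.
- A reader might expect the pilot to supply a counselor ICC for planning. With only a few counselors, such an estimate would be nearly uninformative.
- A reader might apply the same design effect to the TAU groups. Section 1.4.4 describes ongoing groups of several kinds alongside individual sessions. Membership may overlap and turn over, and a formula for fixed, non-overlapping clusters does not fit that.

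**Conclusion.** The point holds in conditional form. Participants in both arms are nested in counselors, the main analysis treats them as independent, and the secondary HLM is not stated to address this. For any positive counselor ICC, the standard errors of the Aim 4 effect sizes are too small and the .05 test is too liberal.

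Under the assumptions above, the understatement runs from negligible to serious, and the protocol does not allow a narrower statement. The central case is a standard error about 14% larger than reported and an error rate of 0.087, or about 0.079 at 80% follow-up. Counselor clustering in TAU would add to this.

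Nothing here shows bias in the point estimates or calls for replacing the MANOVA. With so few counselors, a random counselor effect would be too unstable to serve as the primary model.

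**What to change.** Keep the MANOVA and its point estimates as primary, and make two additions.

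1. Add the treating counselor, for both MICRA and SWNARC participants, to the Participant Enrollment Log in section 5.4 and to the analysis dataset. This is best done during enrollment and treatment, because the listed log fields and the recording labels would not allow it to be reconstructed.
2. Add to section 7.5 a sensitivity analysis that repeats the standard errors and tests with each arm's variance inflated by 1 + (m − 1) × ICC, for ICC 0.01, 0.05 and 0.10. Here m is the average number of analyzed participants per counselor in that arm. Apply it at counselor level only, not to the TAU groups.

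The cost is one extra field and one extra table. The downside is that the stated uncertainty will be wider. Sample size, allocation and treatment procedures are unchanged.

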### **1.3 Participant Eligibility**

The inclusion criteria will be: (1) Southwest Native American tribal member, (2) resident within the Southwest Native American reservation or neighboring small settlements, (3) aged 18 or older, (4) seeking treatment for a substance use disorder, (5) meets current DSM-IV diagnostic criteria for substance abuse or dependence for at least one of the following: alcohol, amphetamine, cannabis, cocaine, or inhalants (including ocean), and (6) willing and able to understand and voluntarily participate (in English) in assessment and treatment procedures of the study. Exclusion criteria are: (1) any planned absences from Southwest Native American tribe greater than 14 days during the 16 week treatment period, (2) cannot identify at least one “locator” person for follow-up tracking, (3) actively psychotic or chronic mental illness that is not well treated, or (4) major cognitive impairment.

## **1.4 Behavioral Interventions**

### **1.4.1 Motivational Interviewing**

Motivational interviewing (MI) is a clinical style originally developed and tested in the treatment of substance use disorders (Miller & Rollnick, 1991, 2002). It draws particularly upon the client-centered counseling methods described by Carl Rogers and his students, to evoke personal motivation for change. It is collaborative rather than authoritarian, emphasizing listening rather than telling, with empathic interest in the other's values and perspective. The MI style is usually well-accepted by Native American groups, resembling normative communication styles within tribal populations.

As a free-standing intervention, MI is relatively brief, usually 1-4 sessions. It can also be conceived, however, as a general clinical style within which other interventions can be delivered. The NIAAA-funded COMBINE study, for example, tested a Combined Behavioral Intervention that used MI both as an initial induction and as the overall clinical style while drawing upon a menu of cognitive-behavioral treatment methods related to the community reinforcement approach (Anton et al., 2006).

### **1.4.2 The Community Reinforcement Approach**

The community reinforcement approach (CRA) to addiction treatment, introduced by Nathan Azrin three decades ago (Hunt & Azrin, 1973) reasoned that to compete with a potent reinforcer like substance use there must be similarly potent, enduring, and reliable sources of reinforcement for non-use. Azrin made some use of extinction and punishment (e.g., via disulfiram, family withdrawal when drinking, refusal to shield from negative consequences), but relied primarily on establishing competing community-engaged sources of positive reinforcement.

Drawing on a flexible menu of procedures, CRA particularly focuses on engaging clients in their own community, in activities and groups that compete with substance use and provide positive reinforcement and/or social support for abstinence. Concerned significant others (CSOs) play an important role in CRA, being important sources of positive reinforcement and social support. By working with existing family and community structures to support and reinforce personal change, CRA would seem to

interface well with existing Native American social structures that engender personal behavioral change. While the family is often the first line of intervention, the additional Clan and Society social structures in the Southwest Native American tribe provide CRA with unique intervention possibilities that are not widely available outside of Native American communities.

### 1.4.3 MICRA

The MICRA intervention will average 16 to 20 sessions and include elements of both MI and CRA. Sessions will be individual, in the sense of one identified client rather than group therapy, but we anticipate high involvement of significant others in these sessions. MICRA will be manual-guided, but specific content will not be prescribed session by session. MI will be used as a front-end induction (1-2 sessions) to engage participants in treatment. It will also be used as a guiding style throughout treatment. The CRA portion of treatment will consist of a menu of procedures that the counselors and clients can choose from to meet the client's needs. CRA will seek to increase sources of positive reinforcement for non-use and engage the client in positive social activities. A primary goal in MICRA will be to re-engage clients in extended family, clan, community, and (if applicable) society activities and responsibilities.

The HIV/STD component of MICRA will be integrated throughout treatment and will be consistent with MI and CRA. This component will not be the main focus of treatment sessions, but will be woven throughout so that participants understand the relationship between substance use and risky sexual behavior. For example, using an MI style, counselors might discuss with participants how sexual behavior and substance use are related. In line with CRA, counselors might complete a functional analysis of situations that lead to risky sex. The MICRA team will decide on the specific components of the HIV/STD prevention piece so that it is congruent with Southwest Native American values.

### 1.4.4 Treatment as Usual

Southwest Native American Recovery Center (SWNARC), the sole outpatient substance abuse treatment program in the Southwest Native American tribe, will serve as the treatment as usual (TAU) comparison for this study. Treatment provided by the Southwest Native American Recovery Center is fairly consistent in its approach. The intake staff assess all clients. Detailed histories are gathered, individual cases are staffed, and clinical assignments are made. Clients are assigned to counselors who have openings; there is no attempt to match client to counselor, other than with an eye towards gender. Treatment starts with individual sessions. Soon thereafter the client joins ongoing group sessions. The clinical staff usually runs group sessions (90 minutes on average), and they engage clients with a reflective style, encouraging them to share their stories regarding substances. Newer group members are generally quiet. From time to time, elder Southwest Native Americans will come to the group meeting and discuss either their personal struggle with substance abuse, or share Southwest Native American perspectives on treating all things - including the self- with respect. Examples of ongoing groups

include a men's group, women's group, arts and crafts group, and Triple A dance group. Individual counseling sessions (60 minutes on average) consist of listening and implementing a generally didactic style that compares current behavior with desired behavior, current situation with optimal situation. Individual sessions occur once weekly, but may happen more frequently if an individual is in crisis. 12 step principles are presented at SWNARC, but more in spirit than in substance. Family members are usually not included in counseling sessions. Individual sessions also review Southwest Native American traditional teachings, showing the client his or her place within the framework of Southwest Native American life. Three cultural educators are part of the SWNARC staff. Release from substance abuse treatment is based on clinical judgment. While clients can spend up to a year at SWNARC, the average length of treatment is two months.

The Center's Director, [name], approximates that 65% of their patient referrals come from the Southwest Native American Tribal Court Systems, 25% from the local IHS (Indian Health Services) Hospital in the Southwest Native American tribe, and the remainder are self-referred. Client flow per month ranges from 70-90, with 30% (lower bound estimate of 21) of those referred under the age of 18 years and approximately 70% (lower bound estimate of 49) over the age of 18 years. Of the 70% over the age of 18, approximately 80% (lower bound estimate of 56) of referrals are men and 20% (lower bound estimate of 14) are women.

### **1.5 Assessments**

Assessment and data collection for MICRA has been designed to consider the temporal needs of measuring changes that may result from behavioral interventions. Initial screening will focus on participant eligibility and reasons for participation or nonparticipation. Baseline and follow-up assessment domains include substance use and related consequences, psychosocial functioning, sexual behavior, psychiatric symptoms, condom use self-efficacy, cultural identity, microaggressions, and future orientation.

Follow-up assessments will take place at 4, 8, and 12 months after the intake assessment (Phase 1 has follow-ups only at 4 and 8 months). Please refer to Chapters 4 and 6 for a more detailed description of the assessments.

### **1.6 Study Size and Duration**

The research assistant will consent nine participants referred from Southwest Native American Recovery Center to participate in MICRA during Phase 1. The research assistant will consent and complete a baseline interview with 80 participants referred from Southwest Native American Recovery Center during Phase 2. These 80 participants will be randomized to MICRA or TAU.

Phase 1 participants and Phase 2 participants randomized to MICRA will receive 16 to 20 therapy sessions over the course of 16 weeks. Phase 2 participants randomized to TAU will receive outpatient treatment at SWNARC. Phase 1 participants will have follow-up assessments at 4 and 8 months; Phase 2 participants will have follow-up assessments at 4, 8, and 12 months.

